9.2 Expedited Adverse Event Reporting

Expedited AE reporting will utilize the descriptions and grading scales as described in *Common Terminology Criteria for Adverse Events v 3.0 (CTCAE)*. SAEs that occur in this study must be promptly reported to the study P.I. ([name]) as well as to the NYU IRB and to the NYU Clinical Trials Office for reporting to the NYUCI Data Safety Monitoring Committee.

9.3 Routine Adverse Event Reporting Guidelines

The IRB Reportable Events Forms (available electronically at http://irb.med.nyu.edu/sites/default/files/irb2/app.reportable.event_.2012.03.07.docx) will be used for all adverse events

10 CORRELATIVE/SPECIAL STUDIES

10.1 Blood Collection for TGF-beta 1 Polymorphism Determination

Approximately 30 mL of blood will be obtained by venipuncture once before starting treatment and once on the last day of treatment, after the last dose of radiation. The specimen will be aliquoted and stored for future testing of other polymorphisms and other related research studies.

10.2 Lymphocyte Isolation, DNA Extraction, PCR Amplification and DNA Sequencing

The lymphocyte isolation and DNA extraction and DHPLC procedures will be performed as previously described (Iannuzzi, Atencio et al. 2002) using the Wave™ DNA Fragment Analysis System manufactured by Transgenomic. Any samples that appear, based upon the DHPLC screening, to be homozygous for either the -509C→T or +869T→C TGF-β1 polymorphism, will be subjected to DNA sequencing using an automated DNA sequencer.

10.3 Test Method

The products of the PCRs will be subjected to DHPLC analysis with the 96 well plate placed in the DHPLC apparatus. The Wave™ DNA Fragment Analysis System (Transgenomic), which will be used for this project, represents a complete unit for the automated DHPLC analysis of PCR products using a DNAsep cartridge specifically designed for separation of DNA fragments. DHPLC is a high throughput technique in which large numbers of DNA samples can be rapidly screened for base sequence alterations and relies upon the physical changes in DNA molecules induced by mismatched heteroduplex formation during reannealing of wild type and mutant DNA.

In this method, a portion of a gene is amplified using standard PCR conditions and the products analyzed using DHPLC. Material from a homozygous sample will only form one species, the wild-type homoduplex. However, when the PCR products produced from a sample

Protocol Type / Version # / Version Date Version 5.4 06/30/2017

heterozygous for a base sequence alteration are heated to 95°C, and then slowly cooled, the DNA strands separate and randomly reanneal to form a mixture of four species; a mutant homoduplex, two heteroduplexes and a wild type homoduplex. When mutant and wild-type DNA strands reanneal to form a heteroduplex, the molecule is physically altered. At the region of base pair mismatches, a "bubble" forms yielding a short linear region of single-stranded DNA. This structural alteration provides the basis for separation of heteroduplex from homoduplex species and ultimately identifies samples with mutant alleles. The basis of this technique is that by heating the column during separation, it is possible to partially denature the sample and elute the homoduplexes and heteroduplexes separately. Heteroduplexes, having a greater percentage of single-stranded DNA than homoduplexes in the mismatch region at a given temperature, will elute first from the column. Therefore, if the DNA sample does not possess a base sequence alteration, only homoduplexes will form and there will be only one peak on the chromatogram representing the homogenous nature of the fragment. A sample that contains a heterozygous mutation will appear as 2, 3 or 4 peaks representing the two homoduplex and heteroduplex populations.

It is also important to note that samples homozygous for a polymorphic allele can readily be detected using DHPLC by adding a roughly equal amount of DNA to the PCR from a sample known to be homozygous for the normal allele, thus essentially creating a potentially "heterozygous" sample.

The first step in the process to detect the -509C→T and +869T→C TGF-β1 gene polymorphisms will be to design primers for amplification of these regions following which the DHPLC buffer and temperature conditions will be optimized for detection of these polymorphisms. For each sample, the PCRs will be performed first without the addition of DNA from a sample that is known to be homozygous for the normal allele, and then, depending upon the DHPLC results, with the addition of known wild type DNA.

For samples in which DNA homozygous for the normal allele was not added, one peak in the DHPLC will indicate it is homozygous for either the wild type or polymorphic allele, whereas multiple peaks will signify it is heterozygous. Next, the PCRs will be performed a second time for all of the putative homozygotes to determine for which allele they are homozygous. Thus, DNA homozygous for the normal allele will be added to the PCR. If there is still one peak in the DHPLC, this will indicate that it is homozygous for the normal allele, whereas if there are multiple peaks, this will signify that the subject is homozygous for the polymorphic allele. All samples which appear to be homozygous for the polymorphic allele will be subjected to DNA sequencing to confirm this assignment.

An important step in this process will be a determination of the appropriate amount of homozygous normal allele DNA to be added to the PCR. Therefore, a titration will be performed with different concentrations of DNA to determine the amount for clearest detection of a sample homozygous for the polymorphic allele.

10.4 Denaturing High Performance Liquid Chromatography (DHPLC)

The mutation screening technique to be used in this study will be denaturing high performance liquid chromatography or DHPLC (Huber, Oefner et al. 1993; Huber, Oefner et al. 1993; Kuklin, Munson et al. 1997; Oefner and Underhill 1998). DHPLC is a robust technique that can be used to screen any gene in a large population for single nucleotide substitutions, as well as small deletions and insertions. Subjects that are either homozygous or heterozygous for a particular allele can both be identified using DHPLC. The advantage of DHPLC is that it enables the rapid, sensitive, accurate and inexpensive identification of polymorphisms and mutations in an automated fashion. Of greatest importance for this project is the evidence that DHPLC possesses a sensitivity and specificity for mutation detection approaching 100% (Liu, Smith et al. 1998; O'Donovan, Oefner et al. 1998; Arnold, Gross et al. 1999; Choy, Dabora et al. 1999; Gross, Arnold et al. 1999; Jones, Austin et al. 1999; Wagner, Stoppa-Lyonnet et al. 1999; Nickerson, Weirich et al. 2000; Taniguchi, Krishnadath et al. 2000) and that this approach possesses greater sensitivity than gel-based assays.

The sensitivity and accuracy of DHPLC for detection of genetic alterations was probably best demonstrated by a quality control study (Bernstein, Teraoka et al. 2003) performed by the WECARE (Women's Environment, Cancer and Radiation Epidemiology) Study Collaborative Group. There are four international laboratory centers (including the laboratory of [name], a co-investigator in this project) that are in the process of screening more than 2000 breast cancer patients for mutations and polymorphisms in a variety of genes associated with DNA repair and radiation responses. The purpose of this quality control study was to investigate the sensitivity and specificity of DHPLC for the detection of *ATM* mutations and polymorphisms. A panel of 19 DNA samples consisting of 4 unaffected controls, 2 heterozygous carriers, and 13 ataxia telangiectasia patients was supplied in a blinded fashion to each of the four laboratories and screened using DHPLC. Prior screening by Single-Strand Conformation Polymorphism (SSCP) and Protein Truncation Test (PTT) had detected 19 mutations among these samples; 18 of these were detected by DHPLC, an efficiency of 95%. In addition to these 18 mutations, DHPLC screening identified 6 new mutations not detected in prior screening. No mutations were identified in control samples by DHPLC, nor were there excess mutations identified in any ataxia telangiectasia patient or carrier sample, suggesting a low rate of false positives.

10.5 Coding of Samples

Specimens will be given a Study ID number and will be otherwise de-identified for privacy protection. The study data manager will keep the list of samples. Any residual blood specimen after performing the listed laboratory studies will be destroyed.

11.2 Use of NYU Facilities

Therapy will be administered in the Department of Radiation Oncology at the Clinical Cancer Center and at Tisch Hospital.

11.3 Conflict of Interest

There are no conflicts of interest to declare.

12 STUDY CALENDAR

Study Procedure	Pre Treatment	Weekly	Last week	Post Treatment (day 45 - 60)	Post Treatment (once/year)
History & Physical	X				
Mammogram and/or breast MRI ^a	X				X ^b
Lumpectomy pathology report	X				
BREAST-focused exam, KPS	X	X		X	X
Lymphedema assessment	X		X		X
Blood for TGF-BETA Polymorphisms and other related research studies	X		X ^c		
Quality of Life Questionnaires ^d	X		X	X	X
LENT/SOMA assessment ^e					X
Thyroid Testing (TSH, T4)	X				X

- a. Standard mammogram or MRI for both breasts.
- b. At each follow-up visit beginning 1 year after completion of radiation treatment a non invasive measurement of fibrosis in the treated breast will be performed using clinical breast exam.
- c. Last day of treatment, after last dose of radiation
- d. QOL will be assessed using the RTOG validated self-assessment questionnaires QLB & QLF (see Appendix 3) at baseline, week 3, day 45 - 60 and 2-yr follow-ups.
- e. Patients will be seen after completion of treatment at day 45 - 60 and then yearly for 5 years total follow up to assess long term sequelae by LENT/SOMA scale.

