2.8.2 Quantitative Measurement of Lymphedema

Patients will be assessed for lymphedema at baseline, end of treatment, and at yearly intervals after completion of radiotherapy. Arm circumference at sites 10 cm above and below the antecubital fossa will be obtained. Mild, moderate, and severe lymphedema is defined as a difference of 0.5 to 2 cm, 2.1 to 3 cm, and greater than 3 cm, respectively, of arm circumference at one or more measurement sites on the treated versus untreated side. Lymphedema progression is defined as transition from lower to higher grade at any time point. Similar lymphedema classification systems have been used in previously published studies (Keramopoulos, Tsionou et al. 1993; Bar Ad, Cheville et al. 2009).

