14 STATISTICAL CONSIDERATIONS

14.1 Endpoints/Objectives:

The primary objectives of this study are to:

1. To evaluate feasibility of prone IMRT to breast, level I- III (includes Cohort A) and supraclavicular nodes (physics and dosimetry parameters).
2. To estimate acute toxicity of prone IMRT to breast, level I- III (includes Cohort A) and supraclavicular nodes

Secondary objectives are to:

1. estimate the incidence of re-simulation to improve dosimetry after initial prone set-up
2. evaluate changes in QOL of patients assessed at baseline and after treatment
3. estimate incidence of late radiation toxicity (e.g., lymphedema, fibrosis and telangiectasia) and to examine genetic determinants of breast fibrosis

Exploratory objectives include:

Estimation of local recurrence rates; estimation of median disease-free survival; estimation of median time to progression, and estimation of median overall survival time.

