APPENDIX 1 – COMMON TOXICITY CRITERIA

Acute Toxicity from *Common Terminology Criteria for Adverse Events v3.0 (CTCAE)*, Published: August 9, 2006

	Grade 0	Grade 1	Grade 2	Grade 3	Grade 4
FATIGUE	No change	Mild fatigue over baseline	Moderate or causing difficulty performing some ADL	Severe fatigue interfering with ADL	Disabling
RADIATION DERMATITIS	No change	Faint erythema or dry desquamation	Moderate to brisk erythema; patchy moist desquamation, mostly confined to skin folds and creases; moderate edema	Moist desquamation other than skin folds and creases; bleeding induced by minor trauma or abrasion	Skin necrosis or ulceration of full thickness dermis; spontaneous bleeding from involved site
PAIN	No pain	Mild pain not interfering with function	Moderate pain; pain or analgesics interfering with function, but not interfering with ADL	Severe pain; pain or analgesics severely interfering with ADL	Disabling

Table 1. RTOG/EORTC and LENT/SOMA classification of late effects

RTOG/EORTC	Grade 1	Grade 2	Grade 3	Grade 4
Skin	Slight atrophy, pigmentation change, some hair loss	Patchy atrophy, moderate telangiectasia, total hair loss	Marked atrophy, gross telangiectasia	Ulceration
Subcutaneous tissue	Slight induration (fibrosis), and loss of subcutaneous fat	Moderate fibrosis, but asymptomatic; slight field contracture, $\leq 10\%$ linear reduction	Severe induration and loss of subcutaneous tissue, field contracture, $\geq 10\%$ linear reduction	Necrosis
LENT/SOMA				
Breast				
Subjective				
Pain	Occasional and minimal Hypersensation, pruritus	Intermittent and tolerable	Persistent and intense	Refractory and excruciating
Objective				
Telangiectasia	$<1\text{ cm}^2$	$1\text{--}4\text{ cm}^2$	$>4\text{ cm}^2$	
Fibrosis	Barely palpable, increased density	Definite increased intensity and firmness	Very marked density, retraction, and fixation	
Edema	Asymptomatic	Symptomatic	Secondary dysfunction	
Retraction, atrophy	10–25%	$>25\text{--}40\%$	$>40\text{--}75\%$	Whole breast
Ulcer	Epidermal only, $<1\text{ cm}^2$	Dermal only, $>1\text{ cm}^2$	Subcutaneous	Bone exposed, necrosis
Lymphedema, arm circumference	2–4-cm increase	$>4\text{--}6\text{-cm}$ increase	$>6\text{-cm}$ increase	Useless arm
Skin				
Pigmentation change	Transitory, slight	Permanent, marked	—	—

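### LENT/SOMA has no pre-radiotherapy score, so the incidence of late breast toxicity cannot be fully separated from change left by surgery and is open to upward bias

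*Combined protocol and SAP*

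**What the plan says.** - Section 2.8 names LENT/SOMA as the scale for reporting late radiation morbidity.
- In Section 12 the row "LENT/SOMA assessment ^e" is marked only in the yearly post-treatment column. Footnote e adds a day 45-60 visit, "then yearly for 5 years total follow up to assess long term sequelae by LENT/SOMA scale". All of these visits follow radiotherapy.
- Footnote b says: "At each follow-up visit beginning 1 year after completion of radiation treatment a non invasive measurement of fibrosis in the treated breast will be performed", by clinical breast exam.
- The same calendar gives a pre-treatment mark to lymphedema, thyroid tests, quality of life and the row "BREAST-focused exam, KPS". No grading scale is named for that exam.
- Section 9.1 calls toxicity late if it occurs more than 60 days after the first day of treatment. It has no change-from-baseline rule.
- Section 14.1 makes it a secondary objective to "estimate incidence of late radiation toxicity (e.g., lymphedema, fibrosis and telangiectasia) and to examine genetic determinants of breast fibrosis". Section 14.3 covers baseline descriptives and the primary endpoints and has no analysis rule for late toxicity.
- Section 2.8.5 gives the genomic endpoint as grade 3 and 4 late complications at 3 years.
- Section 2.8.2 covers arm lymphedema separately: "Patients will be assessed for lymphedema at baseline, end of treatment, and at yearly intervals after completion of radiotherapy".

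**The concern.** Section 6 requires all breast surgery to be finished before entry. Patients arrive after segmental mastectomy, sometimes with re-excision, or after mastectomy, sometimes with reconstruction (Section 7.1). The LENT/SOMA breast items in Appendix 1 grade what is found on the day. Grade 2 fibrosis, for example, is "Definite increased intensity and firmness", and retraction or atrophy is a percentage. A firm scar or volume defect present before the first fraction can therefore receive a grade at year 1, with no earlier grade to compare it with. The study is single-arm, so no comparator removes the surgical background either.

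This matters because Section 2.5 itself warns that acceleration could raise late complications, and the late-toxicity rate is the study's check on that. The synopsis also lists late effects among the primary endpoints. Section 2.5 further cites arm edema in 38.2% after total mastectomy with radiotherapy and 39.1% after total mastectomy alone. That is a different item, but it shows that surgery alone can produce a late effect at a similar rate.

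**Working it through.** The documents give no rate, sample size or power for LENT/SOMA fibrosis, retraction, breast edema or pain, so there is no stated figure to reproduce. The check has three parts.

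**1. Does anything else in the plan supply the missing baseline or an attribution rule?**

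- Toxicity form (Appendix 2): it asks for toxicity due to radiation, but covers only fractions 1-15 and the day 45-60 visit, and only fatigue, dermatitis and breast pain. It does not reach the late period.
- Pre-treatment breast exam (Section 12): done, but no scale is named.
- Baseline questionnaire QLB (Appendix 3): completed after consent, with items on hardening, scar tissue, swelling and pain that recur on the follow-up form. This is useful, but it is patient-reported, is not a LENT/SOMA grade, and no rule links it to late-toxicity scoring.
- Arm circumference (Section 2.8.2): measured at baseline, so lymphedema is outside the problem.

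**2. Size of the bias in incidence.**

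Let p be the true radiation-related rate and b the share already at the counted grade from surgery and still there at follow-up. Assume the two are independent. Then

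observed rate = 1 - (1 - p)(1 - b), and excess = b(1 - p).

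Both p and b are assumptions. With p = 10%:

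- b = 5%: 1 - 0.90 × 0.95 = 14.5%. In 104 patients that is 15.1 instead of 10.4. The share not due to radiation is (14.5 - 10)/14.5 = 31%.
- b = 10%: 1 - 0.90 × 0.90 = 19.0%, share 47%.
- b = 15%: 1 - 0.90 × 0.85 = 23.5%. In 104 patients that is 24.4, share 13.5/23.5 = 57%.

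With p = 5%, the observed rate is 6.9% at b = 2%, 9.8% at b = 5% and 14.5% at b = 10%.

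**3. Size of the dilution in the genetic analysis.**

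Inputs from Section 2.8.4: odds ratio 3.4 for the -509T allele, and severe fibrosis in 15 of 103 (14.6%). Assumptions: carrier frequency 0.3-0.5, the allele odds ratio applied to carriers, surgical background unrelated to genotype, and a background of 1-5% because only grade 3-4 counts under Section 2.8.5.

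Worked case (carrier frequency 0.3, overall rate 14.6%, b = 5%):

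- True risks that satisfy both the overall rate and the odds ratio: about 9.5% in non-carriers and 26.4% in carriers.
- After adding b: 1 - 0.905 × 0.95 = 14.1% and 1 - 0.736 × 0.95 = 30.1%.
- Observed odds ratio: (0.301/0.699)/(0.141/0.859) = 2.6.

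Over carrier frequencies 0.3-0.5:

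| True overall rate | b = 1% | b = 2% | b = 5% |
|---|---|---|---|
| 14.6% | 3.1-3.2 | 2.9-3.0 | 2.5-2.6 |
| 5% | 2.7-2.8 | 2.3-2.5 | 1.8-1.9 |

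The effect is toward 1. It does not create a false association.

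**The case against.** A reader might infer that surgical changes are in fact counted as late radiation toxicity and as cases in the genetics work, and that the damage is beyond repair. The documents do not support that.

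- **Counting.** Nothing says surgical change is counted. What is missing is a rule to exclude it.
- **Genetics.** Section 2.8.5 requires grade 3 or 4 at 3 years. Appendix 1 grade 3 fibrosis means very dense, retracted and fixed tissue, so an ordinary firm scar at year 1 would not be a case. A reader could assume 6% risk in non-carriers and a 10% surgical background and get an odds ratio of 1.9, but that background is not limited to grade 3-4. The genetic work is also exploratory, on stored blood, and Section 14.3 contains no genetic test. It remains true that Sections 1.2.3 and 14.1 state the fibrosis objective without a grade. If that version were analysed, the dilution would apply more fully.
- **Repair.** The pre-treatment exam and QLB could identify some pre-existing change, so the problem is partly recoverable. They still do not yield a LENT/SOMA grade.
- **Importance.** No test or stopping rule uses these LENT/SOMA items, and the bias overstates harm and does not hide it. This limits the severity. It does not make the estimate a radiation-toxicity incidence.
- **The remedy has its own bias.** Under Section 3.1.6, simulation may fall within 60 days of surgery when no systemic therapy is given. Early postoperative edema, pain or induration could raise the baseline, heal, and then mask radiation fibrosis of the same grade. A baseline grade 3 fibrosis can never worsen on a scale whose fibrosis entries stop at 3. This stands, and it rules out using worsening as the only outcome.

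**Conclusion.** The gap is real. With no pre-radiotherapy LENT/SOMA score, a time-only definition, prior surgery in all patients and no comparator, the plan cannot fully separate surgical from radiation-related fibrosis, retraction or atrophy, breast edema and pain. The incidence estimate is open to upward bias of b(1 - p): 14.5-23.5% reported against a true 10% if b is 5-15%. Those inputs are illustrative, and the bias shrinks if surgical change resolves before the follow-up visit.

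The genetics consequence is dilution and probably modest under the Section 2.8.5 endpoint: about 2.5-3.2 in place of 3.4 at the 14.6% severe-fibrosis rate and an assumed 1-5% severe background. It would be larger if severe fibrosis were rarer. Arm lymphedema and its monitoring in Section 14.5 are unaffected. The change is worth making because it is cheap, but neither the primary analysis nor any stopping rule depends on it.

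**What to change.** - **Section 12:** add a pre-treatment mark for LENT/SOMA (breast and chest wall items), scored at the breast-focused exam already scheduled. Also reconcile footnote e, which lists a day 45-60 LENT/SOMA visit, with the row, which has no mark there.
- **Section 14.3:** report late fibrosis, retraction, edema, pain and telangiectasia in two ways: as absolute grade, and as worsening of at least one grade over the pre-treatment score.
- **Genetic analysis:** keep the Section 2.8.5 definition (grade 3-4 at 3 years) and reconcile it with the ungraded objective in Sections 1.2.3 and 14.1. Add a sensitivity analysis that excludes or adjusts for patients already at that grade before radiotherapy. Do not make worsening the sole outcome.

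**Cost:** one extra form at an existing visit, plus wording in these sections. Patients already enrolled will lack the score, so the change-based result covers later patients only. For the earlier patients, the QLB items and the pre-treatment exam notes can support a partial check. Early postoperative change at baseline can mask later radiation change, which is why absolute grade must be reported as well.

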13 DATA REPORTING / REGULATORY CONSIDERATIONS

13.1 Monitoring Plan

An internal Data and Safety Monitoring Committee (DSMC) of the NYUCI is the monitoring board for this study. The committee will review safety at scheduled intervals (not less than once/year) and at the time of planned interim analyses described in Section 9 according to the NYUCI DSMC Charter.

13.2 Stopping Rules (for the individual patient and for the study as a whole)

If safety concerns arise, the DSMC will identify these concerns and recommend modification or termination of the clinical trial. In case of grade 3 acute skin toxicity, the dose per fraction of the remaining treatment fractions will be reduced to 2 Gy/fraction until completion. The clinical trial will be stopped early if regional nodal recurrence is greater than expected (5% of patients) as described in Section 14.

